## 8 Safety and Adverse Events

### 8.1 Definitions

#### 8.1.1 Adverse event definitions

**Adverse effect.** Any untoward medical occurrence in a clinical study of an investigational device; regardless of the causal relationship of the problem with the device or, if applicable, other study treatment or diagnostic product(s).

**Associated with the investigational device or, if applicable, other study treatment or diagnostic product(s).** There is a reasonable possibility that the adverse effect may have been caused by the investigational device or, if applicable, the other study treatment or diagnostic product(s).

**Disability.** A substantial disruption of a person's ability to conduct normal life functions.

**Life-threatening adverse effect.** Any adverse effect that places the subject, in the view of the investigator-sponsor, at immediate risk of death from the effect as it occurred (i.e., does not include an adverse effect that, had it actually occurred in a more severe form, might have caused death).

**Serious adverse effect.** Any adverse effect that results in any of the following outcomes: death, a life-threatening adverse effect, inpatient hospitalization or prolongation of existing hospitalization, a persistent or significant disability/incapacity, or a congenital anomaly/birth defect.

- **Hospitalization** shall include any initial admission (even if less than 24 hours) to a healthcare facility as a result of a precipitating clinical adverse effect; to include transfer within the hospital to an intensive care unit. Hospitalization or prolongation of hospitalization in the absence of a precipitating, clinical adverse effect (e.g., for a preexisting condition not associated with a new adverse effect or with a worsening of the preexisting condition; admission for a protocol-specified procedure) is not, in itself, a serious adverse effect.

**Unexpected adverse effect.** Any adverse effect, the frequency, specificity or severity of which is not consistent with the risk information described in the clinical study protocol(s) or elsewhere in the current IDE application, as amended.

#### 8.1.2 Unanticipated adverse device effect (UADE)

**Unanticipated adverse device effect (UADE).** Any serious adverse effect on health or safety or any life-threatening problem or death caused by, or associated with, a device, if that effect, problem, or death was not previously identified in nature, severity, or degree of incidence in the investigational plan or IDE application (including a supplementary plan or application), or any other unanticipated serious problem associated with a device that relates to the rights, safety, or welfare of subjects.

### 8.2 Recording of Adverse Events

Clinical study subjects will be questioned about adverse effects at study visits. The visits will be documented in the clinical records. Adverse effects with suspected causal relationship to study procedures, determined by the PI or co-I, will be recorded on study adverse effects forms and summarized in CRFs.

### 8.3 Reporting of Adverse Device Effects and Unanticipated Problems

#### 8.3.1 Investigator reporting: Notifying the study sponsor

##### 8.3.1.1 Sponsor contact information for reporting purposes

Report adverse device effects by phone and facsimile to: [name], [contact]; [contact]; [name], [contact]

All observed or volunteered adverse effects (serious or non-serious) and abnormal test findings, regardless of treatment group, if applicable, with suspected causal relationship to the investigational device or, if applicable, other study treatment or diagnostic product(s) will be recorded in the subjects' case histories. For all adverse effects, sufficient information will be pursued and/or obtained so as to permit (i) an adequate determination of the outcome of the effect (*i.e.*, whether the effect should be classified as a *serious adverse effect*) and; (ii) an assessment of the casual relationship between the adverse effect and the investigational device or, if applicable, the other study treatment or diagnostic product(s).

Adverse effects or abnormal test findings felt to be associated with the investigational device or, if applicable, other study treatment or diagnostic product(s) will be followed until the effect (or its sequelae) or the abnormal test finding resolves or stabilizes at a level acceptable to the investigator-sponsor.

#### **8.3.1.2 Abnormal test findings**

An abnormal test finding will be classified as an *adverse effect* if one or more of the following criteria are met:

- The test finding is accompanied by clinical symptoms.
- The test finding necessitates additional diagnostic evaluation(s) or medical/surgical intervention; including significant additional concomitant drug or other therapy. (Note: simply repeating a test finding, in the absence of any of the other listed criteria, does not constitute an adverse effect.)
- The test finding leads to a change in study dosing or exposure or discontinuation of subject participation in the clinical study.
- The test finding is considered an adverse effect by the investigator-sponsor.

#### **8.3.1.3 Causality and severity assessment**

The investigator-sponsor will promptly review documented adverse effects and abnormal test findings to determine (i) if the abnormal test finding should be classified as an adverse effect; (ii) if there is a reasonable possibility that the adverse effect was caused by the investigational device or, if applicable, other study treatment or diagnostic product(s); and (iii) if the adverse effect meets the criteria for a *serious adverse effect*.

If the investigator-sponsor's final determination of causality is "unknown and of questionable relationship to the investigational device or, if applicable, other study treatment or diagnostic product(s)", the adverse effect will be classified as *associated with the use of the investigational device or study treatment or diagnostic drug product(s)* for reporting purposes. If the investigator-sponsor's final determination of causality is "unknown but not related to the investigational device or, if applicable, other study treatment or diagnostic product(s)", this determination and the rationale for the determination will be documented in the respective subject's case history.

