OxyChip removal	The OxyChip will be removed at the time of surgical resection, which will occur within 52 weeks from the time of implantation. Surgery date must be at least three days after placement of the OxyChip. Tumor tissue surrounding the implanted device will be collected and examined for adverse events (primary) and stored to allow for future evaluation of molecular biomarkers (exploratory).
Oxygen measurements	The goal is for at least 2 oxygen measurements to be taken in the period between the day of OxyChip placement and removal (secondary objective). Note, however, that oxygen measurements are not necessary to determine the presence or absence of any unexpected adverse device events of implanting the OxyChip, for the study's primary goal.

PHASE 1B	
Purpose	
Primary: Safety of the OxyChip during neoadjuvant radiotherapy or neoadjuvant chemotherapy with planned surgical resection as part of standard oncologic therapy.
 
Secondary: Feasibility of oxygen measurements during neoadjuvant radiotherapy or neoadjuvant chemotherapy using the OxyChip.

Patient population	
There will be a total of 30 patients enrolled in Phase 1B.
 
Phase 1B will consist of one cohort of 3 evaluable patients receiving chemotherapy treatment and one cohort of 3 evaluable patients receiving radiotherapy. Only after a full evaluation of the first 3 patients that underwent chemotherapy will additional patients receiving chemotherapy be enrolled. Similarly, only after a full evaluation of the first 3 patients that underwent radiotherapy will additional patients receiving radiotherapy be enrolled. The decision to enroll additional patients in each cohort will be made by the study PI after review of surgical pathology reports and after the 3 evaluable patients are greater than 2 weeks after surgical removal of the OxyChip. The two cohorts of 3 patients in Phase 1B are independent of each other, so either of these cohorts may continue accrual after the initial 3 patients while the other is still accruing for the initial 3 patients.
 
In addition, the following eligibility and exclusion criteria will apply:
 
 
• If a patient is to receive neoadjuvant chemotherapy or radiotherapy at a hospital other than DH prior to resection of the cancer at DH, patients
 

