### **8.4 Stopping Rules**

The study will be stopped for any grade 3 or higher toxicity. The study will not re-open until the event is analyzed and deemed to be unrelated to the OxyChip or oxygen measurements.

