## **10 Study Monitoring, Auditing, and Inspecting**

### **10.1 Study Monitoring Plan**

This study will be monitored by the Data Safety Monitoring and Accrual Committee (DSMAC) of the Norris Cotton Cancer Center (NCCC) of Dartmouth-Hitchcock Medical Center. The Clinical Cancer Review Committee (CCRC) of NCCC determines the frequency of DSMAC review. The DSMAC meets quarterly to review accrual rates and information about studies that have accrued participants, including adverse device effects. The DSMAC has the authority to suspend or to recommend termination to the CCRC of all research

activities that fall within its jurisdiction. In the event that a study is suspended or terminated, that information will be forwarded to the responsible IRB office.

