# **12 Publication Plan**

As of now, there is no industry sponsor for this study. The OxyChip-based clinical EPR trial has been developed by the study investigators at Dartmouth. We plan to publish results from this study in peer-reviewed journals with all investigators who participate in the study as co-authors. The primary investigators, Drs. [name] and [name], will have the responsibility for publication.

Neither the complete nor any part of the results of the study carried out under this protocol, nor any of the information provided by the sponsor for the purposes of performing the study, will be published or passed on to any third party without the consent of the primary investigators. Any investigator involved with this study is obligated to provide the primary investigators with complete test results and all data derived from the study.

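### Relatedness of grade 3+ events feeds the primary endpoint, cohort progression and re-opening, yet only study investigators judge it, and events called unrelated need not reach the CRF or the DSMAC

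*Combined protocol and SAP*

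**What the plan says.** - **Endpoint (3.2).** CTCAE grade 3+ toxicities count when they are put down to the device or procedure. The section does not say who attributes them.
- **First screen (8.2).** "Adverse effects with suspected causal relationship to study procedures, determined by the PI or co-I, will be recorded on study adverse effects forms".
- **Causality determination (8.3.1.3).** "The investigator-sponsor will promptly review documented adverse effects and abnormal test findings to determine", among other things, "if there is a reasonable possibility that the adverse effect was caused by the investigational device". A doubtful relationship is treated as associated for reporting purposes. An event of unknown cause that is held to be unrelated has its rationale written in the subject's case history.
- **Progression (7.1, 3.1).** Section 7.1 makes moving on depend on unexpected adverse events, their severity and whether the OxyChip caused them. The PI decides on the second Phase 1A cohort. For Phase 1B, "The decision to enroll additional patients in each cohort will be made by the study PI after review of surgical pathology reports". The Phase 1A step from 6 to 30 turns on unacceptable toxicity, which is not defined, and no decider is named.
- **Stopping (8.4).** Any grade 3+ toxicity stops the study, whatever its cause. "The study will not re-open until the event is analyzed and deemed to be unrelated to the OxyChip or oxygen measurements". The sentence does not say who deems it so.
- **Oversight (10.1).** The DSMAC meets quarterly, reviews accrual and "information about studies that have accrued participants, including adverse device effects", and can suspend the study. No role in attribution, expansion or re-opening is written for it.

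**The concern.** In Phase 1B every patient receives radiotherapy or chemotherapy and is then due for surgery, so a grade 3+ event will often have several plausible causes. The study has a single arm, and everyone judging causality knows that the patient carries a chip. Section 12 adds that the trial "has been developed by the study investigators at Dartmouth". Under 8.4 an unrelated finding is the only stated way back to accrual, so the pressure on a borderline call runs one way.

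None of this implies bad faith. The trouble is that the same judgement supplies the safety result and helps decide whether the study continues, and no independent party is assigned to look at it. If events called unrelated are also missing from the CRF, the attribution cannot easily be re-examined at analysis.

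**Working it through.** **Step 1. Where relatedness enters, and who decides.**

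| Decision | Does relatedness matter? | Named decider | Independent review stated? |
|---|---|---|---|
| Primary endpoint (3.2) | Yes, by definition | None in 3.2; investigator-sponsor via 8.3.1.3 | No |
| Phase 1A, first 3 to next 3 (3.1) | No; any adverse event on examination or pathology | PI | No |
| Phase 1A, 6 to 30 (3.1) | Through 7.1; the toxicity term is undefined | None | No |
| Phase 1B, each cohort beyond 3 (3.1) | Through 7.1 and the Study Summary | PI | No |
| Stop (8.4) | No; any grade 3+ toxicity | Automatic | Not needed |
| Re-opening (8.4) | Yes, sole stated condition | None | No |

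**Step 2. Where an event judged unrelated goes.**

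| Route | Condition for entry |
|---|---|
| Adverse-effect forms and CRF summary (8.2) | Suspected causal relationship |
| FDA report (8.3.1.4) | Unanticipated adverse device effect |
| IRB report (8.3.2) | Associated with the device, and serious, and unexpected |
| DSMAC (10.1) | Named safety input is adverse device effects; nothing stated for other events |
| Case history (8.3.1.3) | Rationale kept when the cause is unknown but held unrelated |

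The stop in 8.4 is triggered by a wider set of events (any cause) than 8.2 requires to be recorded (suspected cause). The trigger therefore has no matching data requirement.

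**Step 3. What one call is worth.** The plan gives no target rate, precision or confidence limit, so there is no safety figure to reproduce. The enrolment totals agree: 3 + 3 + 24 = 30 in Phase 1A, and 30 + 30 = 60 overall.

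One-sided exact (Clopper-Pearson) 95% upper limit:
- For 0 events in n, U = 1 − 0.05^(1/n). With n = 30, U = 9.5%; with n = 60, U = 4.9%.
- For 1 event in n, U solves (1 − U)^n + nU(1 − U)^(n−1) = 0.05. With n = 30, U = 14.9%; with n = 60, U = 7.7%.

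Moving one event from related to unrelated lowers the limit by 14.9 − 9.5 = 5.4 percentage points within a phase, or 7.7 − 4.9 = 2.8 points over all 60.

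**Step 4. Effect on a three-patient Phase 1B gate, under assumptions.** Suppose the gate is read as no attributed event in 3 patients. Let p be the true rate of device-related events and s the share of them that are attributed. The chance of passing is (1 − ps)³.

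| p (assumed) | s = 1 | s = 0.75 | s = 0.5 |
|---|---|---|---|
| 10% | 0.90³ = 72.9% | 0.925³ = 79.1% | 0.95³ = 85.7% |
| 20% | 0.80³ = 51.2% | 0.85³ = 61.4% | 0.90³ = 72.9% |

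Neither p nor s comes from the documents. The table shows only how far under-attribution would loosen a gate this small.

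**The case against.** A reader might infer something stronger: that one person alone controls the endpoint, every gate and re-opening, while the DSMAC sees only events already called device effects. The documents do not support that.

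- Section 8.2 names the PI or a co-investigator. Co-investigators, protocol staff, non-study physicians and pathology also supply assessments (5.2.5, 5.3, 6.3, 6.7).
- The first Phase 1A gate has no attribution wording, and the stop in 8.4 fires whatever the cause. A wrong call cannot avoid a stop; it can only help to end one. That the investigator-sponsor decides re-opening is an inference from 8.3.1.3.
- Section 10.1 lists device effects with the word 'including', which is not exclusive, and gives the DSMAC power to suspend.
- Section 8.3.1.3 sets a low threshold for causality and leans towards association when in doubt.
- Section 10.2 provides monitors who are not involved in the study and who compare records with source. It also invokes a centre-wide monitoring plan, which is not among the documents and may route more events to the DSMAC. Section 8.5 calls for regular review of serious events without limiting it to related ones.
- Section 1.5 reports a maximum CTCAE grade of 1 and no grade 3+ toxicity caused by the chip. The plan bases progression on clinical judgement, not on a confidence limit.

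These points rule out the stronger reading. They do not close the gap. Co-investigators are still study investigators. The lean towards association is stated for reporting and is applied by the same party. The monitors' stated scope is compliance, data quality and study integrity, not causality, and the serious-event review in 8.5 is the PI's responsibility. A power to suspend helps only if the event reaches the committee, and this protocol states no duty to send it.

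**Conclusion.** The point holds as a gap in oversight and data capture, and it should be fixed. Relatedness of grade 3+ events shapes the primary result, progression and re-opening; only study investigators judge it; two of the decisions have no named decider; and an event judged unrelated has no required place on the CRF and no stated path to the DSMAC.

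The size is modest and conditional: one reclassified event is worth 5.4 percentage points on the one-sided upper limit within a phase of 30. How many such calls will arise cannot be derived, because the documents give no any-cause grade 3+ rate. It would go too far to say that a misjudgement would set the primary result to zero; that needs every related event to be misclassified. Nothing in the documents suggests that any event has been misjudged so far.

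The conclusion assumes that the centre-wide monitoring plan cited in 10.2 does not already send all grade 3+ events to the DSMAC. If it does, the protocol need only say so, and what remains is to name the deciders and widen the CRF.

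**What to change.** - **8.2:** record every grade 3+ event on the CRF, whatever its cause, with the investigator's causality call and a short rationale.
- **8.4 and 10.1:** send every grade 3+ event, whatever its attribution, to the existing DSMAC. Name who decides on re-opening, and require the DSMAC's documented concurrence, out of cycle if needed, before the study re-opens.
- **3.1:** require the same concurrence before any Phase 1B cohort expansion still pending. Section 1.6.2 shows the six-patient Phase 1A stage to be complete, so for that gate it is enough to document who took the decision and on what basis.
- **3.2 and 7.1:** keep investigator attribution for the endpoint. Report all grade 3+ events regardless of attribution beside it, and list any on which the DSMAC disagreed.

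Replacing the investigators' attribution with the DSMAC's as the endpoint is not needed; its merits are debatable, and it would in effect add an assessor.

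The cost is protocol and CRF wording, some out-of-cycle work for the committee, and a possible delay of some days to re-opening or expansion. The committee's capacity for out-of-cycle review should be confirmed, since the protocol describes only quarterly meetings. No sample size or stated number changes.

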#### **8.3.1.4 Reporting of adverse effects to the FDA.**

The investigator-sponsor will submit a completed [FDA Form 3500A](#) to the FDA's Center for Devices and Radiological Health for any observed or volunteered adverse effect that is determined to be an *unanticipated adverse device effect*. A copy of this completed form will be provided to all participating sub-investigators.

The completed [FDA Form 3500A](#) will be submitted to the FDA as soon as possible and, in no event, later than 10 working days after the investigator-sponsor first receives notice of the adverse effect.

If the results of the sponsor-investigator's follow-up evaluation show that an adverse effect that was initially determined to not constitute an *unanticipated adverse device effect* does, in fact, meet the requirements for reporting; the investigator-sponsor will submit a completed [FDA Form 3500A](#) as soon as possible, but in no event later than 10 working days, after the determination was made.

For each submitted [FDA Form 3500A](#), the sponsor-investigator will identify all previously submitted reports that that addressed a similar adverse effect experience and will provide an analysis of the significance of newly reported adverse effect in light of the previous, similar report(s).

Subsequent to the initial submission of a completed [FDA Form 3500A](#), the investigator-sponsor will submit additional information concerning the reported adverse effect as requested by the FDA.

### **8.3.2 Reporting of adverse effects to the responsible IRB**

In accordance with applicable policies of the Dartmouth College's Institutional Review Board (IRB)—the Committee for Protection of Human Subjects (CPHS)—the investigator-sponsor will report, to the IRB, any observed or volunteered adverse effect that is determined to meet all of the following criteria: (i) *associated with the investigational device or, if applicable, other study treatment or diagnostic product(s)*; (ii) *a serious adverse effect*; and (iii) *an unexpected adverse effect*. Adverse event reports will be submitted to the IRB in accordance with the respective IRB procedures.

Applicable adverse effects will be reported to the IRB as soon as possible and, in no event, later than 10 working days after an investigator learns of the effect.

Follow-up information to reported adverse effects will be submitted to the IRB as soon as the relevant information is available. If the results of the sponsor-investigator's follow-up investigation show that an adverse effect that was initially determined to not require reporting to the IRB does, in fact, meet the requirements for reporting; the investigator-sponsor will report the adverse effect to the IRB as soon as possible, but in no event later than 10 working days, after an investigator learns of the effect.

#### **8.3.2.1 Withdrawal of IRB approval**

The Sponsor shall notify the FDA, all participating IRBs and participating investigators of any withdrawal of approval of the study by a reviewing IRB within 5 working days after receipt of the withdrawal of approval.

#### **8.3.2.2 FDA reporting process**

Medical Device Reports, whether for anticipated or unanticipated device-related effects, are to be submitted on FDA Form 3500A (MEDWATCH Form). The contact information for submitting MDR reports is noted below:

Food and Drug Administration  
Center for Devices and Radiological Health  
Medical Device Reporting  
[name]  
[name]

### **8.4 Stopping Rules**

The study will be stopped for any grade 3 or higher toxicity. The study will not re-open until the event is analyzed and deemed to be unrelated to the OxyChip or oxygen measurements.

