## 1.6 Justification of cohort design and revisions of the protocol

### 1.6.1 Rationale for expanding Phase 1A and Phase 1B Cohorts

Pilot studies for medical devices are intended to test the initial design of the device and procedures. It is expected that device modifications or procedure modifications will be made based on the experience of various providers in real clinical scenarios during the testing phase. The following are some reasons for conducting a pilot study for medical devices and how a larger study (*i.e.*, a more typical pilot study size of up to 30 patients) will be important for studying the safety and performance of the OxyChip.

We will initiate Phase 1A (oxygen measurements without therapy planned prior to surgical resection) with two cohorts of 3 patients. The table below provides justification to expand the Phase 1A study from these two cohorts of 3 patients to then enroll an additional 24 patients if no unacceptable toxicities including unanticipated adverse device effects (UADE) occur in the first 6 patients.

Goal	Phase 1A - 6 patient study	Benefit to expanding the study
Help address specific safety concerns	The initial 6 patients suggest safety of the device and study procedures in pre-surgical patients, but the study is small.	Increasing the Phase 1A to 30 patients will provide additional safety information for pre-surgical patients prior to proceeding with either a “Pivotal” study or a study combining oxygen measurements with an oxygen treatment for a therapeutic stud.
Permit initial assessment of device design	Initial device design suggests that the device and procedures are well tolerated.	Additional designs of the EPR measuring device (not in the OxyChip itself) are planned to help identify the OxyChip more efficiently in patients and in tumor specimens.
Better define/refine the clinical endpoints and intended patient population		Additional patients will allow more measurements of specific tumor types ( e.g. , skin SCC, melanomas and SCC of the head and neck region) to collect baseline pO 2 and oxygen responsiveness in larger cohorts of these tumor types.
Provide investigators with initial device experience and identify special training needs	All injections were performed by only two clinicians, [name] and [name].	Expanding the trial will allow more investigators to be trained in injection procedures. Specifically, [name] will be trained to perform injections.

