Patient population	
There will be a total of 30 patients enrolled in Phase 1A.
 
Initially, 3 patients will be enrolled; the OxyChip will be placed; physical examination of the site will be made periodically (at least in conjunction with visits where oxygen measurements will be made) starting from one day following implantation for up to 52 weeks – at which point the tumor will be resected with concurrent removal of the OxyChip. If no adverse events are noted in the physical exams or tissue pathology, an additional 3 patients will be enrolled in this phase of the study. The decision to start the second cohort of 3 will be made by the study PI after review of surgical pathology reports and after the first 3 evaluable patients are at a time point more than 2 weeks following surgical removal of the OxyChip. Next, if no unacceptable toxicity is noted after completion of the first 6 patients, the enrollment will be open to 24 more, for a total of 30 patients. (Note: the enrollment totals will include patients enrolled at DHMC or Emory University, once the addition of Emory as a participating site is approved.)
 
In addition the following eligibility and exclusion criteria will apply:
 
 
• Superficial tumors located <math>\leq 3</math> cm from skin or mucosal surface.
 
• Surgical resection of the tumor is planned at least 3 days following implantation.
 
• Eligible tumors for this phase of the protocol are any tumors that (a) are identified by imaging or physical exam to be superficial enough for OxyChip placement and (b) will receive surgical resection with intent to remove the entire tumor.
 

	
 
• Previous radiation to the site is not allowed.
 
• Planned use of chemotherapy or radiation therapy or use of angiogenesis inhibitor prior to resection is not allowed.
 
• Patients do not have to agree to an oxygen measurement in order to be eligible. Although oxygen measurements are desirable, the primary endpoint is safety of the OxyChip placement and removal over a short time frame.
 
• Tumors must be <math>\geq 2.5</math> cm in minimum diameter to be eligible.
 

OxyChip placement	Placement of OxyChip will be through a minimally invasive procedure (see methods for implantation protocol ).

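### The 8.4 stopping rule names only grade 3+ toxicity, so after the expansion checkpoints a UADE not rated grade 3+ triggers no automatic pause, although 1.6.1 treats a UADE as a bar to expansion

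*Combined protocol and SAP*

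**What the plan says.** - **Stopping (8.4).** "The study will be stopped for any grade 3 or higher toxicity". Then: "The study will not re-open until the event is analyzed and deemed to be unrelated to the OxyChip or oxygen measurements". This is the only study-wide stopping rule, and UADE does not appear in it.
- **Expansion rationale (1.6.1).** Phase 1A may enroll "an additional 24 patients if no unacceptable toxicities including unanticipated adverse device effects (UADE) occur in the first 6 patients". A UADE is counted here as a kind of unacceptable toxicity.
- **Operative checkpoint (3.1 schema).** "if no unacceptable toxicity is noted after completion of the first 6 patients, the enrollment will be open to 24 more". UADE is not named. Phase 1B requires a full evaluation of the first 3 patients per modality, and UADE is not named there either.
- **Primary objective (2.1).** UADE is listed among the effects to be assessed and reported.
- **Statistical plan (7.1).** Proceeding with each cohort depends on unexpected adverse events, their severity and their attribution to the OxyChip. No grade threshold is given.
- **Definitions (8.1.1, 8.1.2).** Seriousness is set by outcome (death, threat to life, hospital admission of any length, disability, birth defect). The UADE definition adds a residual limb: "or any other unanticipated serious problem associated with a device that relates to the rights, safety, or welfare of subjects".
- **Handling of a UADE.** An FDA report is due "in no event, later than 10 working days after the investigator-sponsor first receives notice of the adverse effect" (8.3.1.4), and 8.3.2 sets a similar limit for the IRB. Section 8.5 gives the PI safety oversight and sets monthly calls. Section 10.1: "The DSMAC has the authority to suspend or to recommend termination to the CCRC of all research" activities within its remit. That committee meets quarterly.

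**The concern.** Expansion and stopping rest on different event lists. The first turns on UADE (1.6.1) or on unexpected attributable events (7.1). The second turns on CTCAE grade. The same event, a UADE rated below grade 3 or not graded at all, would bar expansion under 1.6.1 if it occurred in the first six Phase 1A patients. If it occurred later, no rule pauses implantation for it.

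This is a first-in-human implant study with safety as its primary objective, and much of the new exposure comes after that first checkpoint. The first six Phase 1A patients were limited to 4 weeks of residence, while the 52-week allowance applies to the other 24. Results for the six were already in the 2017 version of the protocol, and fiducials were added in 2019. In Phase 1A, the long-residence allowance and the fiducials therefore fall wholly outside the one checkpoint that names UADE.

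**Working it through.** The plan gives no alpha, power or event rate on this point, so the check is a comparison of text plus cohort arithmetic.

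**1. The criteria side by side**

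| Section | Decision | Criterion | UADE named? |
|---|---|---|---|
| 1.6.1 | Phase 1A, 6 to 30 | Unacceptable toxicity | Yes |
| 3.1, Phase 1A | Same | Unacceptable toxicity, not defined | No |
| 3.1, Phase 1B | Beyond 3 per modality | Full evaluation | No |
| 7.1 | Each cohort | Unexpected, attributable events, no grade | No |
| 8.4 | Study-wide stop | Grade 3+ toxicity | No |

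**2. Events between the two lists.** A UADE escapes 8.4 only if it is not rated grade 3+. Two routes are open on the definitions: an event that is serious by outcome (for example a short admission) but graded lower, and a device problem under the residual limb with no graded toxicity. Section 2.1 itself lists breakage, loss of sensitivity and calibration change. Such a problem is a UADE only if it is also serious and unanticipated.

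**3. What then follows.** Reporting within 10 working days gives notice but does not require a pause. The monthly calls in 8.5 carry no pause criterion. Suspension by the monitoring committee is discretionary. Early removal under 4.4.1 concerns the affected patient, not new implantations.

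**4. Patients enrolled after the checkpoints**
- Plan's own totals: 6 + 24 = 30 in Phase 1A; 30 + 30 = 60 overall. These agree.
- After the checkpoints: Phase 1A 30 − 6 = 24; Phase 1B at most 30 − (3 + 3) = 24.
- Total: 24 + 24 = 48; 48/60 = 80%. This is an upper bound, because the Study Summary caps Phase 1B at 30.

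**5. Chance of at least one such event.** The formula is 1 − (1 − p)^n, where p is an assumed per-patient rate of UADE not rated grade 3+. The documents give no rate, so a range is shown.

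| p | n = 6 | n = 24 | n = 48 |
|---|---|---|---|
| 1% | 5.9% | 21.4% | 38.3% |
| 2% | 11.4% | 38.4% | 62.1% |
| 5% | 26.5% | 70.8% | 91.5% |
| 10% | 46.9% | 92.0% | 99.4% |

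At every rate, such an event is more likely after the checkpoints than in the first six patients, simply because more patients are enrolled then.

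**6. Implantations while waiting.** Planned average accrual is 60 patients / 60 months = 1 per month (planned total over planned duration, not observed accrual).
- Longest wait for a quarterly meeting: 3 × 1 = 3 patients.
- Average wait for an event at a random time: 1.5 × 1 = 1.5 patients.
- If the monthly call led to a pause: at most about 1 patient.

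**7. Re-opening.** Section 8.4 re-opens only after the event is found unrelated to the OxyChip or the measurements. Under 8.1.2 a UADE is caused by, or associated with, a device. A UADE of the OxyChip cannot meet that condition.

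**The case against.** The strongest reply is that other controls exist. The committee reviews adverse device effects and can suspend; its quarterly meeting is not stated to be the only occasion for doing so, and the CCRC sets how often it reviews a study. The PI oversees safety and holds monthly calls. The Study Summary speaks of reviewing each subsequent cohort of 3, and 7.1 has no grade threshold, so both can be read as continuing review. A reader might infer from 8.4 that a UADE below grade 3 halts nothing, or that the later patients are protected by 8.4 alone. The documents do not support either. What survives is that none of these controls is an automatic pause, and that 3.1 sets no checkpoint after the first 6 patients in Phase 1A or the first 3 per modality in Phase 1B.

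Second, most limbs of the UADE definition describe severe events that would probably be grade 3+ anyway, and 8.4 is wider in one respect: it stops for any such toxicity before attribution. This stands and limits the gap, although no section states the mapping from UADE to grade.

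Third, an expansion criterion and a stopping rule may properly differ, and 1.6.1 is a rationale section. That is fair as design, but the plan gives no reason for the difference and leaves unacceptable toxicity undefined in 3.1.

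Fourth, the Introduction binds the study to 21 CFR parts 803 and 812. Whether those parts already require a halt cannot be checked from these documents. The point therefore concerns what the protocol itself states.

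**Conclusion.** The concern holds in limited form. The 8.4 trigger is grade-based only, 1.6.1 counts a UADE as disqualifying, and after the checkpoints in 3.1 no passage requires a pause for a UADE not rated grade 3+. Up to 48 of 60 patients are enrolled in that period.

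The gap is probably narrow, consisting mainly of events serious by outcome but graded lower and of problems under the residual limb. How often these occur is unknown: the rates in the table are assumptions, and 1.5.6 reports no UADE to date. A reader might take 3 further implantations as the expected delay. It is the longest quarterly wait at an assumed average accrual, and PI oversight or the monthly call could shorten it.

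This should be corrected because the inconsistency lies in the safety rule of a safety study and is cheap to remove. It does not show that the study lacks safety oversight.

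**What to change.** Reconcile 8.4 with 1.6.1, 2.1, 3.1, 7.1 and the Study Summary so that one event list serves both expansion and stopping, with UADE as defined in 8.1.2 named in 8.4 consistently with 1.6.1. Define unacceptable toxicity once and refer to it throughout. State whether cohort review continues after the checkpoints in 3.1.

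Reconcile the re-opening sentence in the same amendment. Adding UADE to the trigger alone could close the study permanently, because a UADE of the OxyChip cannot be found unrelated to it. A separate, easier condition for UADE would let a device-related UADE re-open the study while a related grade 3 toxicity could not. The sponsor must set the condition and state it for both kinds of event.

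Report the number of UADEs by phase beside the primary count.

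The cost is small: a revised trigger and re-opening sentence in 8.4, matching references in the other sections, and one line in the safety summary. UADEs are already identified and reported, so no new data are needed. The downside is an occasional accrual pause for a UADE below grade 3.
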